#### **For participants receiving 2M (Q8W) IM injections while on ATLAS 2M:**

After confirming eligibility into the sub-study, participants will enter into the Thigh Injection Phase and receive an intramuscular injection of CAB LA (3 mL; 600 mg) on one lateral thigh and RPV LA (3 mL; 900 mg) into the opposite lateral thigh at the following visits:

- Day 1
- Week 8

Participants will remain in the research unit for at least 2 hours after the injection for post-dose PK sampling and safety assessments.

Participants will then return to the clinic 1 week and 4 weeks after the injection for PK sampling as outlined in Time and Event Table Section [11.13.5.2](#).

#### **11.13.4.4. Return to Gluteal Injection Phase**

#### **For participants receiving monthly (Q4W) IM injections while on A2M**

Participants who received CAB LA + RPV LA IM thigh injection every 4 weeks for a total of 16 weeks during the Thigh Injection Phase will return to the clinic to receive an IM gluteal injection of CAB LA (2 mL; 400 mg) on one lateral thigh and RPV LA (2 mL; 600 mg) into the opposite lateral thigh at the following visits ( $\pm 7$  days):

- Week 16
- Week 20

Q4W participants will complete 8 weeks (2 injection cycles) of CAB/RPV LA and the Week 24 pre-injection assessments after which the participant's participation in the sub-study will conclude (at week 24). The Week 24 injection will be the first injection back on the main study (A2M).

The 2 injection cycles for Q4W dosing during the Gluteal Injection Phase will correspond to 1 injection cycle during the Gluteal Injection Phase for the Q8W dosing participants thereby ensuring similar assessments for both arms (see T&E).

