To assess patient reported outcomes during the thigh injection phase by administering the following health outcome measurements: Numerical Rating Scale (NRS) and HIVTSQ.	
 
• Numerical Rating Scale (NRS): To assess the tolerability of injections during both the Thigh and Gluteal Injection Phase
 
• HIVTSQ (both s and c versions):
 

[figure not shown]
Objectives	Endpoints
	
To measure levels of satisfaction and detect change in satisfaction when switching from gluteal to thigh injections in total “treatment satisfaction” score, and individual item scores of the HIV Treatment Satisfaction Questionnaire (HIVTSQ) during the Thigh Injection Phase as well as the change from thigh during the Return to Gluteal Phase.

To assess participant’s preference of thigh injections during the thigh injection phase compared to gluteal injections.
	
Preference Questionnaire: To assess patient’s preference, and reasons for preference, for injections received during the Thigh Injection Phase compared with prior gluteal injections as well as for injections received during the Return to Gluteal phase compared with prior thigh injections.

Exploratory Endpoints
	

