**11.13.4. Sub-study Amendment Design**

The A2M sub-study will consist of three phases including a Screening Phase (1 injection interval: 4 weeks for Q4W subjects and 8 weeks for Q8W subjects), a Thigh Injection Phase 16 weeks of thigh injections, 4 injection intervals for Q4W and 2 injection intervals for Q8W) and a Return to Gluteal Injection Phase (8 weeks of gluteal injections for both Q4W subjects and Q8W subjects). At the conclusion of the sub-study, participants will have the option to continue on the A2M main study or if commercial access treatment is available, the participant can transition off the sub-study and withdraw from A2M and proceed directly to CAB/RPV LA.

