**For participants receiving 2M (Q8W) IM injections while on A2M:**

Participants, who received CAB LA + RPV LA IM thigh injection every 8 weeks for a total of 16 weeks during the Thigh Injection Phase will return to the clinic to receive an IM gluteal injection of CAB LA (3 mL; 600 mg) on one lateral thigh and RPV LA (3 mL; 900 mg) into the opposite lateral thigh at the following visits:

- Week 16
- Week 24

Q8W participants will complete 8 weeks (1 injection cycle) of CAB/RPV LA and the Week 24 pre-injection assessments after which the participant's participation in the sub-study will conclude (at Week 24). The W24 injection will be the first injection back on the parent study (A2M).

The 1 injection cycle for Q8W dosing during the Gluteal Injection Phase will correspond to 2 injection cycles during the Gluteal Injection Phase for the Q4W dosing participants thereby ensuring similar assessments for both arms (see T&E)

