**11.13.4.5. Sub-study completion**

Participants are considered to have completed the study if they complete pre-dose assessments at sub-study Week 24 visit.

Depending on the local availability of the marketed product in each country, after the sub-study is completed participants will be invited to:

- Countries where CAB LA+RPV LA marketed product is not yet locally available: Continue in the Extension phase of the main study and complete study visits as per Time & Events table in Section [7.1](#)).
- Countries where CAB LA+RPV LA marketed product is locally available: Transition to CAB LA + RPV LA marketed product or an alternative ART as indicated below:
  - i. After the pre-injection assessments are completed at week 24, the participant **will receive the last gluteal injection as part of the main study.**
  - ii. **Participant will complete Safety Follow Up visit** 2-4 weeks after the last injection (please refer to Section [5.6](#) of the Protocol) before transitioning to a marketed ART.

Note: If the participant has to withdraw from the study due to safety related reasons once CAB LA + RPV LA marketed product is locally available (see Section 5.5) the subject would need to complete withdrawal visit and enter in the Long Term Follow Up phase (see Section 4.2.4).

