**Sub-study Footnotes:**

- a. Physical exams should be conducted as part of normal routine clinical care. Medical assessments include any decisions the study staff must make for participants management and/or care of participant.
- b. Measure vital signs after about 5 minutes of rest in a semi-supine position.
- c. A 12-lead ECG will be performed after resting in a semi-supine position for at least 5 minutes. ECGs will be performed pre-dose. A 2-hour post dose ECG will also be performed at sub-study Day1 visit.
- d. All injection visits during the sub-study should kept to the same projected visit schedule as in the parent study.
- e. Women of childbearing potential only. SR=serum, UR=urine. Urine pregnancy test can be performed at study visits when other blood draws are not required in order to limit needle sticks.
- f. A morning specimen is preferred.
- g. An overnight fast is preferred; however, a minimum of a 6-hour fast is acceptable.
- h. Should be collected 30 to 60 minutes post injection
- i. Week 24 IM administration will not be considered part of the sub-study assessments. The IM administration at W24 and any assessments completed after IM administration at this visit will be considered part of the parent study.
- j. PK window allowed for sample collection: For 1-week post dose sample (3 to 10 days post dose), for 4-week post dose sample (+7 days) and for 2-hours post dose samples ( $\pm 1$  hour)
- k. At Week 16, HIVTSQs should be administered before HIVTSQc.
- l. All Patient Report Questionnaires/Surveys - except NRS - will be administered via paper instrument (in exceptional circumstances the questionnaires could be completed via telephonic interview, please refer to COVID19 appendix for additional details) at the beginning of the visit before any other assessments are conducted.

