**11.13.6.2. Sub-study Dosage and Administration**

**NOTE:** All injection visits during the sub-study should kept to the same projected visit schedule as in the parent study.

**Participants receiving monthly (Q4W) IM injections** while on A2M study who enter into the Thigh Injection Phase will receive an intramuscular injection of CAB LA (2 mL; 400 mg) on one lateral thigh and RPV LA (2 mL; 600 mg) into the opposite lateral thigh on Day 1 of the Thigh Injection Phase. Subsequent thigh injections with CAB LA 400 mg and RPV LA 600 mg will occur every 4 weeks ( $\pm 7$  days).

Participants who received CAB LA + RPV LA IM thigh injection every 4 weeks for a total of 16 weeks during the Thigh Injection Phase will return to the clinic 4 weeks later ( $\pm 7$  days) to receive their first IM gluteal injection (at Week 16) of CAB LA (2mL; 400mg) and RPV LA (2 mL; 600 mg) during the Return to Gluteal Injection Phase. The subsequent gluteal injection with CAB LA 400 mg and RPV LA 600 mg will occur 4 weeks later ( $\pm 7$  days) at Week 20. Gluteal injection administered at Week 24 visit will be considered part of the parent study.

The interval between injection visits will be limited to a maximum of 5 weeks. The Medical Monitor must be contacted to discuss individual participant case management if the length of time between injections exceeds or is projected to exceed 5 weeks.

**Participants receiving 2M (Q8W)** IM injections while on A2M study who enter into the Thigh Injection Phase will receive an intramuscular injection of CAB LA (3 mL; 600 mg) on one lateral thigh and RPV LA (3 mL; 900 mg) into the opposite lateral thigh on day 1 of the Thigh Injection Phase. Subsequent thigh injections with CAB LA 600 mg and RPV LA 900 mg will occur every 8 weeks ( $\pm 7$  days).

Participants who received CAB LA + RPV LA IM thigh injection every 8 weeks for a total of 16 weeks during the Thigh Injection Phase will return to the clinic 8 weeks later (at Week 16) to receive their first IM gluteal injection of CAB LA (3mL; 600mg) and RPV LA (3 mL; 900 mg) during the Return to Gluteal Injection phase. The subsequent gluteal injection with CAB LA 600 mg and RPV LA 900 mg will 8 weeks later ( $\pm 7$  days) at Week 24. Gluteal injection administered at Week 24 visit will be considered part of the parent study.

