#### **11.13.6.3. Oral Bridging during the Sub-study**

Given the limited number of thigh injections for both Q4W (4 injections) and Q8W (2 injections) during the sub-study, any oral bridging will not be allowed in this sub-study.

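### Section 11.13.4.4 places the return-phase gluteal injections in the lateral thighs in both arms, contradicting the rest of the thigh sub-study

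*Protocol*

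**What the plan says.** Section 11.13.4.4 gives the dosing for the Return to Gluteal Injection Phase. In the Q4W paragraph, participants "will return to the clinic to receive an IM gluteal injection of CAB LA (2 mL; 400 mg) on one lateral thigh", with RPV LA (600 mg) going into the other lateral thigh, at Weeks 16 and 20. In the Q8W paragraph, participants return "to receive an IM gluteal injection of CAB LA (3 mL; 600 mg) on one lateral thigh", again with RPV LA (900 mg) in the other thigh, at Weeks 16 and 24.

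Elsewhere the sub-study says something different:

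- Section 11.13.4 (design) describes "a Return to Gluteal Injection Phase (8 weeks of gluteal injections for both Q4W subjects and Q8W subjects").
- Section 11.13.6.2 (dosage and administration) has Q4W participants return "to receive their first IM gluteal injection (at Week 16") and treats the following dose as gluteal too. Its Q8W paragraph agrees. It names no thigh site for the return phase.
- The Time and Events tables (11.13.5.1 and 11.13.5.2) head the return-phase columns as gluteal administration.
- Section 11.13.6.3 (oral bridging) refers to the "limited number of thigh injections for both Q4W (4 injections) and Q8W (2 injections").
- On Week 24, section 11.13.4.5 says the participant "will receive the last gluteal injection as part of the main study", and footnote i to the Time and Events tables says "Week 24 IM administration will not be considered part of the sub-study assessments".

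**The concern.** One injection cannot be both gluteal and in the lateral thigh, so the sentence contradicts itself as well as the other sections. The site wording matches that of the Thigh Injection Phase in section 11.13.4.3 and appears to have been carried over. Injection site is the variable this sub-study examines, and 11.13.4.4 is the only section that spells out sides and anatomical sites for the return phase.

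Two secondary health-outcome measures in section 11.13.3 need a real return to gluteal dosing. One is the change in HIVTSQ satisfaction from the thigh phase to the return phase. The other is Preference "for injections received during the Return to Gluteal phase compared with prior thigh injections". For a participant who is still being injected in the thigh, both would compare thigh with thigh. The pain ratings (NRS) at Weeks 16 and 17, injection site reactions after the return injections, and the Week 17 PK sample would also carry the wrong site label.

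Thigh exposure would also run past the 16 weeks over which sections 11.13.2 and 11.13.8.2 plan to assess thigh safety. The supporting Phase 1 data in 11.13.1 are single thigh injections in 14 people.

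**Working it through.** **Step 1. Reproduce the stated count.** The thigh-phase visits listed in section 11.13.4.3 are:

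- Q4W: Day 1 and Weeks 4, 8 and 12 = 4
- Q8W: Day 1 and Week 8 = 2

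Both match section 11.13.6.3.

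**Step 2. Count again with the sites as written in 11.13.4.4.** Only injections belonging to the sub-study are added, so Week 24 is left out.

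| Arm | Thigh phase | Added by 11.13.4.4 | Total | Ratio to stated |
|---|---|---|---|---|
| Q4W | 4 | 2 (Weeks 16, 20) | 6 | 6/4 = 1.5 |
| Q8W | 2 | 1 (Week 16) | 3 | 3/2 = 1.5 |

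The last dosing interval in each arm would end at Week 24, so thigh dosing would cover 24 weeks instead of 16. No sub-study injection after Day 1 would be gluteal.

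**Step 3. Ceiling on exposed visits.** At the 41 participants per arm of section 11.13.8.2: 41 × 2 + 41 × 1 = 82 + 41 = 123 return-phase dosing visits.

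**Step 4. Which visits reach the questionnaire endpoints.** Footnote l to the Time and Events tables has every questionnaire except the NRS completed at the start of the visit. The return-phase HIVTSQs and Preference forms are scheduled at Week 20 (Q4W) and Week 24 (Q8W), so in both arms they reflect the Week 16 injection. The Q4W Week 20 injection comes after the last questionnaire and the last NRS. Of the 123 visits, 41 + 41 = 82 (the Week 16 visits) could therefore alter the HIVTSQ and Preference contrasts. The other 41 could affect only the injection-site-reaction record.

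**Step 5. What is not affected.**

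- Primary PK: in Table 16 the gluteal reference interval is Week -4 (Q4W) or Week -8 (Q8W) to Day 1. The last thigh interval ends at Week 16, with the pre-dose sample.
- Week 17 PK enters none of the comparisons in Table 15.
- The secondary safety and virologic endpoints in 11.13.3 are confined to the thigh phase.
- The gluteal NRS collected at Screening stands.

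**Step 6. Week 24 in the Q8W list.** Section 11.13.4.4 lists Week 24 among the Q8W return-phase injections, then assigns that dose to the parent study in its next paragraph. Section 11.13.6.2 and footnote i also assign it to the parent study, and the Q8W Time and Events row shows no injection at Week 24. The Q4W list correctly leaves it out.

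**The case against.** The strongest reply is that nobody would be misled. The section heading and the disputed sentence both say gluteal, every other section agrees, and section 11.13.6.2 sends sites to the Study Reference Manual for further dosing detail. Participants have had at least 152 weeks on the regimen. The sub-study tests no formal hypothesis and its primary comparison is safe. The figure of 123 visits supposes that every site misreads every visit.

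Much of this stands. The intent is clear, the design is coherent, and 123 is a ceiling with no misreading rate behind it; for the questionnaire contrasts the ceiling is 82. Section 11.13.4.5 is weak support because it concerns only the Week 24 dose. The Week 24 listing is untidy, but the same section largely resolves it.

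The reply does not make the sentence correct. It is current operative text, it is wrong in both arms, and it names a specific wrong body site where site is the factor being compared. A reader can resolve it only by setting it against other sections.

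**Conclusion.** The concern holds: section 11.13.4.4 is wrong as written in both arms and should be corrected. If it were followed literally, thigh injection visits would rise by 50% in each arm (4 to 6 and 2 to 3), and thigh dosing would last 24 weeks instead of 16. Up to 123 sub-study dosing visits are exposed, of which the 82 at Week 16 determine whether the return-phase HIVTSQ and Preference contrasts mean what they say. These figures assume 41 participants per arm and thigh dosing at every return-phase visit. The protocol gives no basis for an expected number and no sign that any site injected the thigh. No primary PK estimate or sample-size figure changes.

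**What to change.** In both paragraphs of section 11.13.4.4, replace the lateral-thigh sites with gluteal ones: CAB LA on one gluteal side and RPV LA on the other. In the Q8W list, delete Week 24 or mark it as a parent-study injection. Send sites a short notice of the correction. If any return-phase injection was given in the thigh, analyse that participant's return-phase data by the site actually used.

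The cost is a wording change in two paragraphs and a site notice. The design, sample size and primary analysis stay as they are.

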**For participants receiving 2M (Q8W) IM injections while on A2M:**

Participants, who received CAB LA + RPV LA IM thigh injection every 8 weeks for a total of 16 weeks during the Thigh Injection Phase will return to the clinic to receive an IM gluteal injection of CAB LA (3 mL; 600 mg) on one lateral thigh and RPV LA (3 mL; 900 mg) into the opposite lateral thigh at the following visits:

- Week 16
- Week 24

Q8W participants will complete 8 weeks (1 injection cycle) of CAB/RPV LA and the Week 24 pre-injection assessments after which the participant's participation in the sub-study will conclude (at Week 24). The W24 injection will be the first injection back on the parent study (A2M).

The 1 injection cycle for Q8W dosing during the Gluteal Injection Phase will correspond to 2 injection cycles during the Gluteal Injection Phase for the Q4W dosing participants thereby ensuring similar assessments for both arms (see T&E)

**11.13.4.5. Sub-study completion**

Participants are considered to have completed the study if they complete pre-dose assessments at sub-study Week 24 visit.

Depending on the local availability of the marketed product in each country, after the sub-study is completed participants will be invited to:

- Countries where CAB LA+RPV LA marketed product is not yet locally available: Continue in the Extension phase of the main study and complete study visits as per Time & Events table in Section [7.1](#)).
- Countries where CAB LA+RPV LA marketed product is locally available: Transition to CAB LA + RPV LA marketed product or an alternative ART as indicated below:
  - i. After the pre-injection assessments are completed at week 24, the participant **will receive the last gluteal injection as part of the main study.**
  - ii. **Participant will complete Safety Follow Up visit** 2-4 weeks after the last injection (please refer to Section [5.6](#) of the Protocol) before transitioning to a marketed ART.

Note: If the participant has to withdraw from the study due to safety related reasons once CAB LA + RPV LA marketed product is locally available (see Section 5.5) the subject would need to complete withdrawal visit and enter in the Long Term Follow Up phase (see Section 4.2.4).

#### 11.13.4.6. Sub-study Amendment Withdrawal/Stopping Criteria

Participants meeting **Withdrawal/Stopping criteria as per Section 5.5** will discontinue the study treatment and be withdrawn from both A2M and the sub-study, and will complete assessments per T&E table in Section 7.1 and enter in the Long Term Follow-Up phase.

Participants who decide to discontinue their participation in the sub-study **for non-safety reasons** (refer to Section 5.5), including participants who require **Oral Bridging** during the sub-study **or** participants who decide to discontinue their participation in the sub-study due to **injection-site (thigh) related tolerability reasons**:

- In countries where the marketed products of CAB and RPV LA are **not yet locally available**, such patients will be allowed to transition back to the main study and continue with IM gluteal injections per the randomized dosing schedule.
- In countries where the marketed products of CAB and RPV LA are **locally available**: patients will be invited to return to gluteal injections in the main study and receive 1 more gluteal injections (additional injections might be required if requested by MM) before transitioning to marketed product as described in Section 4.2.4 and Section 5.6

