### **7.8.1. Value Evidence and Outcomes Endpoints (Secondary)**

- The “Preference” questionnaire will assess preference for CAB LA + RPV LA every 8 weeks or CAB LA + RPV LA every 4 weeks compared to oral ARV regimen, and preference for CAB LA + RPV LA every 4 weeks compared to CAB LA + RPV LA every 8 weeks at Week 48 (or Withdrawal).
- Change from Week 8 in Dimension scores (e.g., “Bother of ISRs”, “Leg movement”, “Sleep”, and “Injection Acceptance”) and individual item scores assessing pain during injection, anxiety before and after injection, willingness to be injected in the future and overall satisfaction with mode of administration over time using the Perception of iNjection questionnaire (PIN) at Weeks 24, 48, and Week 152 (or Withdrawal).
- Proportion of participants considering pain and local reactions following injection to be extremely or very acceptable based on the acceptability score over time using the Perception of iNjection questionnaire (PIN).
- Change from Baseline (Day 1) in total “treatment satisfaction” score, and individual item scores of the HIVTSQs at Weeks 24, 48 and 152 (or Withdrawal).
- Change in treatment satisfaction over time (using the HIVTSQc) at Week 48 (or Withdrawal).
- Change from Baseline (Day1) in treatment acceptance (at Weeks 24, 48 and 152(or Withdrawal from the study) using the “General acceptance” dimension of the Chronic Treatment Acceptance (ACCEPT) questionnaire.
- Change from Baseline (Day1) in HR QoL (using the HAT-QoL short form) at Weeks 24, and 48, (or Withdrawal).

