**11.13.5. Sub-study: Time and Events table**

**11.13.5.1. Sub-study: Time and Events Table for CAB LA + RPV LA Q4 Weekly Administration**

Procedure	Screening Phase d Gluteal administration		Thigh Injection Phase d Q4 Weekly thigh administration						Return to Gluteal Injection Phase d Q4 Weekly gluteal admin.			
	Screening (Week -4)	Week -3	Day1	Week 1	Week 4	Week 8	Week 12	Week 13	Week 16	Week 17	Week 20	Week 24
IM treatment administration i	X		X		X	X	X		X		X	
Written Inform consent	X											
Eligibility Verification (Inclusion/Exclusion criteria)	X											
Symptom directed physical exam and Medical assessment a	X		X		X	X	X		X		X	X
Weight and BMI			X						X			

Procedure	Screening Phase d Gluteal administration		Thigh Injection Phase d Q4 Weekly thigh administration						Return to Gluteal Injection Phase d Q4 Weekly gluteal admin.			
	Screening (Week -4)	Week -3	Day1	Week 1	Week 4	Week 8	Week 12	Week 13	Week 16	Week 17	Week 20	Week 24
Vital Signs, BP, HR, temp b	X		X						X			
Smoking status	X											
12-lead ECG c	X		X						X			
HIV associated conditions	X	X	X	X	X	X	X	X	X	X	X	X
AEs, SAEs, concomitant medications	X	X	X	X	X	X	X	X	X	X	X	X
ISR assessments for IM injections	X	X	X	X	X	X	X	X	X	X	X	X
Clinical Chemistry and Hematology	X		X		X	X	X		X			X
Pregnancy Testing, SERUM c	S		S		S	S	S		S		U	S

Procedure	Screening Phase d Gluteal administration		Thigh Injection Phase d Q4 Weekly thigh administration						Return to Gluteal Injection Phase d Q4 Weekly gluteal admin.			
	Screening (Week -4)	Week -3	Day1	Week 1	Week 4	Week 8	Week 12	Week 13	Week 16	Week 17	Week 20	Week 24
HIV-1 RNA and sample for storage (S)	X		X		X	X	X		X			X
CD4+ cell count	X		X		X	X	X		X			X
CD8+ cell count			X						X			
Urinalysis f			X						X			
Fasting lab assessments: Glucose, Cholesterol (Total, HDL and LDL) and triglycerides g			X						X			
PBMC for storage			X									

Procedure	Screening Phase d Gluteal administration		Thigh Injection Phase d Q4 Weekly thigh administration						Return to Gluteal Injection Phase d Q4 Weekly gluteal admin.			
	Screening (Week -4)	Week -3	Day1	Week 1	Week 4	Week 8	Week 12	Week 13	Week 16	Week 17	Week 20	Week 24

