##### **Intent-to-Treat Exposed Population for Thigh PK Sub-study Amendment**

The ITT-E population for this substudy will consist of all participants who were randomized in the main study and received at least one CAB and/or RPV thigh injection. Participants will be assessed according to their randomized treatment, regardless of the treatment they received. Participants in this population will be included in the efficacy and health outcomes analyses.

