### **11.13.8.4. Key Elements of Analysis Plan**

#### **11.13.8.4.1. Primary Analysis**

The primary analysis is to compare the thigh injection with the gluteal injection using the ratio of the geometric mean of thigh injection to the geometric mean of the gluteal injection for a PK parameter within each treatment arm (Q8W, Q4W) and each analyte (CAB, RPV). The PK parameter comparisons of interest are described in [Table 15](#) of Section [11.13.8.2](#). No formal hypothesis testings will be performed.

Following loge-transformation,  $C_{max}$ ,  $C_{tau}$  and  $AUC(0-tau)$  will be separately analyzed by treatment arm and analyte using a mixed effects model with fixed effect term for type of injection (thigh, gluteal) and random effect term for subject. In each model, only subjects

with PK parameter estimates from corresponding both thigh and gluteal injections are included. For example, in the model for comparing  $C_{max}$  between the first CAB thigh injection vs gluteal CAB injection for Q8W subjects, only Q8W subjects with  $C_{max}$  estimates from both first CAB thigh injection and CAB gluteal injection are included. Point estimates and their associated 90% confidence intervals will be constructed for the differences between the thigh injection and the gluteal injection. The point estimates and their associated 90% confidence intervals from the log-transformed analysis will then be back-transformed to provide point estimates and 90% confidence intervals for the ratios between the thigh injection and the gluteal injection on the original scale.

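### The thigh sub-study schedules no assessment at early discontinuation, so participants who stop for thigh-site tolerability give no post-thigh satisfaction score, and the earlier leavers give no preference answer

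*Protocol*

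**What the plan says.** Section 11.13.4.6 of the Protocol describes two ways out of the sub-study.

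- Participants who meet the Section 5.5 stopping criteria leave both studies and "will complete assessments per T&E table in Section 7.1 and enter in the Long Term Follow-Up phase".
- A second group includes "participants who decide to discontinue their participation in the sub-study due to injection-site (thigh) related tolerability reasons". Where marketed product is not locally available, "such patients will be allowed to transition back to the main study and continue with IM gluteal injections per the randomized dosing schedule". Where it is available, they return to main-study gluteal dosing for at least one injection before moving to it. No exit assessment is named in either case.

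The sub-study Time and Events tables (Sections 11.13.5.1 and 11.13.5.2) run from Screening to Week 24 with no discontinuation column. Both schedule HIVTSQs at Day 1 and Week 16, and HIVTSQc at Week 16 only. A last HIVTSQs follows at Week 20 (Q4W) or Week 24 (Q8W). Preference is asked at Weeks 12 and 20 (Q4W) and at Weeks 8 and 24 (Q8W). Footnote l places all questionnaires except the NRS at the start of the visit.

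Section 11.13.3 sets the Preference endpoint "for injections received during the Thigh Injection Phase compared with prior gluteal injections". Section 11.13.8.3.1 defines the sub-study ITT-E population as those with at least one thigh injection and adds: "Participants in this population will be included in the efficacy and health outcomes analyses".

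**The concern.** Preference and satisfaction are asked only of participants who are still in the sub-study at fixed weeks. One foreseen reason for leaving is that the participant cannot tolerate the thigh site, which is close to what these questions measure. The people most likely to prefer gluteal injections, or to report falling satisfaction, are therefore the likeliest to be missing, and the expected error runs in one direction.

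The main study shows the alternative. In Section 7.8.1 its Preference endpoint carries a withdrawal timepoint ("compared to CAB LA + RPV LA every 8 weeks at Week 48 (or Withdrawal"), as do most of its other questionnaire endpoints. The sub-study has no counterpart.

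The analysis plan cannot repair this later. It can bound or impute missing answers, but it cannot supply answers that the schedule never collected.

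**Working it through.** **1. What each leaver provides, read from the two schedules.** Thigh injections are at Day 1 and Weeks 4, 8 and 12 (Q4W), or Day 1 and Week 8 (Q8W). Pre-dose PK is drawn at Day 1 and Weeks 4, 8, 12 and 16 (Q4W), or Day 1 and Weeks 8 and 16 (Q8W) (Table 14). Table 16 ends the first thigh interval at Week 4 (Q4W) or Week 8 (Q8W), and the last at Week 16.

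| Leaves | Thigh-phase Preference | Post-thigh HIVTSQs/HIVTSQc | First-interval Ctau |
|---|---|---|---|
| Q4W, before the Week 4 visit | no | no | no |
| Q4W, after Week 4 and before Week 12 | no | no | yes |
| Q4W, at or after Week 12 and before Week 16 | yes | no | yes |
| Q8W, before the Week 8 visit | no | no | no |
| Q8W, at or after Week 8 and before Week 16 | yes | no | yes |

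Every row lacks post-thigh HIVTSQ. Preference is missing in three of the five. Anyone who leaves after the last thigh injection but before Week 16 also lacks the sample that closes the last interval.

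**2. Whether the main study fills the gap.** These participants return to the main study; they are not withdrawn from it, so nothing in the text at hand triggers a withdrawal visit when thigh injections stop. Entry requires at least 152 weeks on study (Section 11.13.4.1.1). The main-study questionnaire endpoints (Section 7.8.1) end at Week 152 or withdrawal, as do the analysed PK samples in Table 10. The main-study Preference question compares Q8W, Q4W and oral treatment, not thigh with gluteal.

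**3. The plan's precision figure, then the PK effect.** Section 11.13.8.2 takes a CV of 56% and 41 per arm, and states a 90% half-width within 19% on the log scale, or (0.83, 1.21).

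- SD on the log scale = √ln(1 + 0.56²) = 0.522
- Half-width = 1.645 × 0.522 × √(2/41) = 0.190, giving (0.827, 1.209). The plan's figure reproduces.
- With 37 complete pairs: 1.645 × 0.522 × √(2/37) = 0.200. With 33: 0.212.

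The primary model uses complete pairs (only subjects "with PK parameter estimates from corresponding both thigh and gluteal injections are included"), so a missing closing sample removes the participant from the Ctau and AUC comparison for that interval. The cost in precision is minor.

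**4. Illustration for Preference.** The documents give no stopping rate. Assume that k of 41 leave unanswered, that all k would prefer gluteal, and that a proportion p of responders prefer thigh. The all-treated figure is p × (41 − k)/41, and the responders-only figure is too high by p × k/41. For p = 60%:

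| k | All-treated figure | Overstatement (points) |
|---|---|---|
| 1 | 58.5% | 1.5 |
| 2 | 57.1% | 2.9 |
| 4 | 54.1% | 5.9 |
| 6 | 51.2% | 8.8 |
| 8 | 48.3% | 11.7 |

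For p from 50% to 70% and k from 1 to 8, the overstatement runs from 1.2 to 13.7 points.

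**5. Illustration for HIVTSQc** (total score −33 to 33). The shift in the mean is (k/41) × the gap between those who stay and those who leave. With k = 4 and an assumed gap of 10 points, it is 4/41 × 10 ≈ 1.0 point.

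**The case against.** A reader might infer that participants who stop leave no Preference, HIVTSQ or end-of-interval PK data at all, so that the results describe only those who tolerated the thigh. The schedules do not support that. Everyone has a Day 1 HIVTSQs. Anyone given a second thigh injection has the pre-dose sample closing the first interval. In the Q8W arm, the only thigh injection that can be declined after experience of one is at Week 8, and that visit schedules Preference and pre-dose PK ahead of dosing. A Q8W participant who attends Week 8 as a sub-study visit and declines there has both. The same holds for Preference in a Q4W participant who declines at Week 12.

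Other points against also carry weight:

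- Preference and satisfaction are secondary and no hypothesis is tested (Section 11.13.8.1). The stated main objective in Section 11.13.2 is PK comparability, with similar safety and tolerability.
- Intolerance is not hidden. Injection site reactions are assessed at every visit, NRS pain is recorded from the first thigh injection, and discontinuation due to such reactions is itself a secondary endpoint.
- The only thigh tolerability data shown are from single injections in 14 healthy volunteers: 13 mild reactions and one moderate. They give no basis for a high stopping rate.
- Section 7.5.1 allows extra PK samples, and Section 11.13.8.4.2 leaves health-outcomes detail to the analysis plan.
- The amendment history mentions a Week 152 limit on withdrawal questionnaires. A change log cannot establish the current rule, and the present Sections 5.5 and 7.1 are not in the text at hand. Nothing here rests on that log.

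These points narrow the concern. They do not supply a post-thigh HIVTSQ for anyone leaving before Week 16, or a Preference answer for a Q4W participant who leaves at Week 4 or 8.

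**Conclusion.** The point holds in a limited form. The sub-study has no early-discontinuation assessment, and participants who stop for thigh-site tolerability return to gluteal dosing without one. Those leaving before Week 16 give no post-thigh HIVTSQs or HIVTSQc. Those leaving before the Week 12 visit (Q4W) or the Week 8 visit (Q8W) give no thigh-phase Preference answer. All of them remain in the named analysis population.

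Because the loss is related to the outcome, the preference and satisfaction summaries are likely to be tilted towards the thigh. That direction rests on the reasonable but untested assumption that people who stop for tolerability favour gluteal injections. The size cannot be computed from the documents, and the figures in the working are illustrations under stated assumptions. Closing PK for the interval in which a participant stops may also be unscheduled, but losing 4 of 41 pairs widens the half-width only from 0.190 to 0.200. This is a cheap improvement to secondary, descriptive results and no threat to the primary PK comparison.

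**What to change.** Add a column for discontinuation of thigh injections to both sub-study Time and Events tables, completed at the next scheduled injection visit before the first gluteal injection. It should contain:

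- Preference (thigh versus gluteal), if not already answered;
- HIVTSQs, then HIVTSQc, in the order already set for Week 16;
- the pre-dose CAB and RPV PK sample.

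Refer to this column in Section 11.13.4.6, and state that the values enter the sub-study ITT-E summaries.

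The cost is an amendment to two tables, plus a few questionnaires and one blood sample at a visit that takes place anyway, since sub-study injection visits keep to the parent-study schedule (footnote d). The reported thigh preference may come out less favourable. No dosing or stopping rule changes.
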